# PRecIsion Medicine in CardiomyopathY (PRIMaCY)

Statistical Analysis Plan

July 21, 2020

All statistical analyses were performed using R version 3.4.1 with survival, multiple imputation by chained equations, mboost, riskRegression, and mlr packages. Clinical characteristics were summarized using descriptive statistics. Continuous variables were summarized using median and interquartile range, whereas categorical variables were summarized using frequencies and proportions. The primary outcome was time to an SCD event during 5-year follow-up defined as a composite outcome of SCD, resuscitated sudden cardiac arrest (including sustained VT/ventricular fibrillation), and aborted SCD events, that is, appropriate shock in a patient with a primary prevention ICD. Event-free survival was estimated by using the Kaplan-Meier method as was the cumulative proportion of SCD events over time.

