#### **Model Development and Performance Assessment**

### General Modeling Approach

To generate a risk prediction model, the relative contribution of the clinical and genetic predictors was quantified by using a competing risk model for SCD events with non-SCD death as the competing risk. This analysis was implemented by using cause-specific regression. To ensure that the quantification was pertinent to the clinical context, patients were administratively censored at 5 years from first evaluation. Two models were considered: a clinical-only model and a clinical/genetic model that included genotype status of the patient. Patients harboring a pathogenic/likely pathogenic causal variant on genetic testing, that is, genotype-positive patients, were compared with patients without a causal variant on testing. We applied a model-boosting algorithm to the cause-specific hazard regression to identify and quantify the association between the candidate risk factors and the composite outcome. For continuous risk factors, the associations were modeled without the assumption of linearity using penalized b-splines. The estimated nonlinear associations were summarized graphically. On the fitting of the 2 boosted models, we then obtained the linear predictors and baseline hazard for the SCD events.

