### Model Tuning

To tune the boosting model, we applied 10 repeated 4-fold cross-validations to determine the hyperparameter of the boosting model. In this exercise, we considered a small learning rate (step size) of 0.01 and a large number of steps. Within each cross-validation iteration, we imputed the missing values by using multiple imputation by chained equations before training the model. The plausibility of missing at random assumed in the imputation depends on the candidate risk factors. As long as the candidate risk factors considered in the study are comprehensive, as in our study, this assumption is reasonable. Next, we applied the trained model and calculated the c-statistic on the cross-validation data for each step. The optimal number of steps (ie, the value of the boosting model hyperparameter) was the one that maximized the c-statistic averaged over all cross-validation iterations. The final model was then fitted using all data with the optimal hyperparameter value estimated in the model-tuning exercise. Given the competing risk data, separate cause-specific hazard regression models were fitted and tuned: 1 for SCD events and the other for non-SCD deaths. Because of a small number of patients with non-SCD deaths, we only applied 3-fold cross-validation to identify and quantify the risk factors associated with non-SCD deaths.

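### Spline and two-level terms compete in the same boosting, with base-learner degrees of freedom neither stated nor equalised; unless they were equal, selection tilts away from genotype and other binary factors

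*SAP*

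**What the plan says.** SAP, General Modeling Approach, gives the boosting two jobs, selection and weighting: "We applied a model-boosting algorithm to the cause-specific hazard regression to identify and quantify the association". On the form of the terms it says: "For continuous risk factors, the associations were modeled without the assumption of linearity using penalized b-splines". Two models are fitted, one with clinical factors only and "a clinical/genetic model that included genotype status of the patient". Genotype there is a two-level comparison: pathogenic or likely pathogenic variant against no causal variant. The section's stated aim is to measure how much clinical and genetic predictors each contribute.

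SAP, Model Tuning, adds that "we considered a small learning rate (step size) of 0.01 and a large number of steps", that "we applied 10 repeated 4-fold cross-validations to determine the hyperparameter of the boosting model", and that the chosen number of steps "was the one that maximized the c-statistic averaged over all cross-validation iterations". The opening paragraph names the software, "using R version 3.4.1 with survival, multiple imputation by chained equations, mboost, riskRegression, and mlr packages", without base-learner settings.

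The SAP does not give the spline df, penalty or knots, the df of the binary terms, any split into linear and non-linear parts, any mandatory term, or any report of selection frequencies. Protocol section 5 does not mention boosting.

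**The concern.** Component-wise boosting adds, at each step, the single term that most reduces the residual error. A flexible term fits noise better than a stiff one, so it wins more often even when neither factor matters. A two-level factor has one slope. A spline under the usual second-difference penalty leaves its linear part unpenalised, so any allowance for curvature gives it more than one slope df. Equal competition therefore needs a deliberate choice, and the SAP describes none.

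Protocol section 1.3 asks for a calculator built on clinical and genetic factors, and the two SAP models differ only by genotype. If base-learner settings hold genotype back, a small gain from adding it could reflect those settings rather than its prognostic value. Binary clinical factors listed in Protocol section 3.1, such as syncope and family history, would be affected in the same way.

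**Working it through.** **Sizing from the documents.** Protocol section 5 expects 3,000 screened, 70-80% eligible, and a 6% event rate given as 100-150 events.
- Eligible: 3,000 × 0.70 = 2,100 to 3,000 × 0.80 = 2,400. The simulations use the midpoint, 2,250.
- Events: 2,100 × 0.06 = 126 to 2,400 × 0.06 = 144, consistent with the stated range.

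The documents give no figure for df, selection frequency or genotype weight. Spline df, candidate numbers and true effects below are assumptions.

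**Mechanism.** Let u be the current residuals and S the smoother matrix of a base-learner. The term picked maximises u'(2S − S'S)u. If u is pure noise with variance σ², the expected reduction is σ² × trace(2S − S'S). Residuals are centred, so the intercept contributes nothing. A binary term scores σ² × 1. A spline with d df counted with the intercept, under the trace(2S − S'S) definition, scores σ² × (d − 1): 1.2, 1.5, 2, 3 and 5 times σ² at d = 2.2, 2.5, 3, 4 and 6. If df means trace(S), the same nominal d gives a looser spline and a larger tilt.

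**First pick, no true effects, 6 continuous and 6 binary candidates.** Share going to any binary factor (fair: 50%), over repeated runs, the larger with 1,500 and 2,400 replicates:

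| Spline df (with intercept) | df = trace(S) | df = trace(2S − S'S) |
|---|---|---|
| 2.2 | 40-42% | 45% |
| 2.5 | 30-33% | 38% |
| 3 | 19-20% | 27-28% |
| 4 | 8-10% | 14-15% |
| 6 | 1-2% | 3% |

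The 1,500-replicate run is placed under trace(S) because its results match that column. A 300-replicate run gave 28% and 7% under trace(S) at 2.5 and 4 df, within simulation error. A 600-replicate run gave 39.8% and 14.3% at 2.5 and 4 df, close to the second column. With all terms at 1 df (each spline split into linear plus centred deviation) it gave 48.5%.

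**Dependence on the candidate set.** Genotype's own first-pick share with 6 binary candidates (600 replicates):

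| Continuous candidates | Fair | 4 df | 2.5 df | Equal df |
|---|---|---|---|---|
| 3 | 1/9 = 11.1% | 4.7% | 10.0% | 11.7% |
| 6 | 1/12 = 8.3% | 2.8% | 6.3% | 7.7% |
| 9 | 1/15 = 6.7% | 1.7% | 4.8% | 6.5% |

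**After tuning.** Cox boosting with 6% events (2,250 × 0.06 = 135) and genotype prevalence 50%. Simplifications: one 4-fold cross-validation instead of 10 repeats, step 0.1 instead of 0.01, at most 1,500 steps, no missing data or competing deaths. There were 100 replicates at hazard ratios (HR) 1.0 and 1.25, and 80 at 1.5 and 2.0. Spline df 4 against equal df:

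| True HR (log) | Genotype ever selected | Mean log HR | Ratio | Paired difference (SE) |
|---|---|---|---|---|
| 1.0 (0) | 10% vs 21% | 0.001 vs 0.007 | – | −0.006 (0.004) |
| 1.25 (0.223) | 32% vs 49% | 0.046 vs 0.089 | 52% | −0.043 (0.008) |
| 1.5 (0.405) | 65% vs 82% | 0.140 vs 0.214 | 65% | −0.074 (0.009) |
| 2.0 (0.693) | 97% vs 100% | 0.404 vs 0.481 | 84% | −0.077 (0.011) |

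At HR 1.5 the share of the truth is 0.140/0.405 = 35% against 0.214/0.405 = 53%. A separate simulation at HR 1.5 with 420 replicates per setting gave retention of 63% against 74% and 34% against 44% of the truth. Selection of each null spline factor fell from 46-50% to 34-37%.

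**How much of the attenuation is due to df.** At HR 1.5 the shortfall is 0.405 − 0.140 = 0.265 with unequal df and 0.405 − 0.214 = 0.191 with equal df, so 0.191/0.265 = 72% remains after the fix. In the separate simulation, 66 points are missing before and 56 after: 56/66 = 85% remains.

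**The case against.** The strongest objection is that unequal df is assumed. The SAP is short, it names a package without settings, and its silence does not show that the terms were unequal. With equal df the tilt disappears. This stands, and it is why the point is conditional. A reader might infer that genotype was in fact picked far too rarely and that its weight in the calculator is understated. The documents do not support that, since they neither show unequal competition nor rule it out.

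Second, the most striking figures concern the first step with no true effects, whereas the calculator comes from a tuned path. That also stands. The tuned effect is moderate at HR 1.25-1.5 and nearly absent for selection at HR 2. Equal df also let a null genotype in more often (21% against 10%), although its mean coefficient was then only 0.007.

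Third, most of the shrinkage is early stopping, which affects every factor. This is true, but both settings were tuned and stopped by the same rule, so the paired differences isolate what the df setting adds.

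Fourth, no harm to prediction has been shown. In a simulation at HR 1.5 (561 paired replicates, 4-fold tuning, step 0.3, at most 300 steps), equal df raised the genotype log HR from about 0.17 to 0.22. The c-statistic in new data changed by about 0.0002 (SE about 0.0004). That run had about 187 events, more than the Protocol expects, and it too rests on assumed predictors. It is still enough to rule out any claim here that discrimination suffers.

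What survives is that the SAP sets out to quantify genotype's contribution, and the base-learner df affect that quantity.

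**Conclusion.** The point holds in conditional form. The stated method puts undecomposed penalised splines and a two-level genotype term into one competition without equalising or reporting their df. If they were unequal, selection tilts toward continuous factors, slightly near 2 df and strongly at 4 or more. A modest genotype effect (HR 1.25-1.5) is then retained less often and given less weight: at HR 1.5, retention of about 63-65% against 74-82%, and a log HR of about 35% against 44-53% of the truth.

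The consequence is for the relative contribution attributed to genotype and other binary factors, not for overall discrimination. The sizes are illustrative. They depend on the assumed df and its definition, the candidate set, a real genotype effect, and simplified tuning. At 80 replicates the standard error of a 65% retention figure is √(0.65 × 0.35/80), about 5 points. The direction was the same in every run with a true genotype effect and at every unequal df tested.

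**What to change.** Give every base-learner the same df. Enter each continuous factor as a 1-df linear term plus a 1-df centred spline deviation, and enter genotype and the other binary factors at 1 df. State the df, whether the intercept is counted, and which trace definition is used. As sensitivity analyses, report selection frequencies for all candidates and a clinical/genetic fit with genotype as a mandatory term. If the df were already equal, saying so and adding the sensitivity analyses is enough.

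Cost: no new data are needed. The SAP is written in the past tense, however, so the change probably means rerunning the imputation and 10 × 4-fold tuning, refitting, and repeating the validation. Curvature enters more slowly and the path is longer: in the HR 1.5 simulation the median stopping point rose from 620 to 1,250 steps.

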### Model Tuning

To tune the boosting model, we applied 10 repeated 4-fold cross-validations to determine the hyperparameter of the boosting model. In this exercise, we considered a small learning rate (step size) of 0.01 and a large number of steps. Within each cross-validation iteration, we imputed the missing values by using multiple imputation by chained equations before training the model. The plausibility of missing at random assumed in the imputation depends on the candidate risk factors. As long as the candidate risk factors considered in the study are comprehensive, as in our study, this assumption is reasonable. Next, we applied the trained model and calculated the c-statistic on the cross-validation data for each step. The optimal number of steps (ie, the value of the boosting model hyperparameter) was the one that maximized the c-statistic averaged over all cross-validation iterations. The final model was then fitted using all data with the optimal hyperparameter value estimated in the model-tuning exercise. Given the competing risk data, separate cause-specific hazard regression models were fitted and tuned: 1 for SCD events and the other for non-SCD deaths. Because of a small number of patients with non-SCD deaths, we only applied 3-fold cross-validation to identify and quantify the risk factors associated with non-SCD deaths.

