1.3 OBJECTIVES

1. To develop and validate a SCD risk calculator that is age-appropriate for children with HCM that includes clinical and genetic factors

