### Model Performance

On model fitting, both prognostic index and the 5-year cumulative proportion of SCD events were quantified for each patient. The discriminatory power of the final model was quantified using the c-

statistic for competing risk models. Model calibration was assessed by stratifying patients into 3 risk groups based on tertiles of the predicted 5-year probability of a SCD event and by creating a calibration curve to show the relationship between the observed and predicted 5-year probability of events.

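### The number of boosting steps is tuned on the c-statistic alone, which cannot see the spread of the absolute 5-year risks that the calculator reports

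*SAP*

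**What the plan says.** Under General Modeling Approach, the SAP boosts cause-specific hazard regressions, with penalised splines for continuous factors, and extracts the linear predictor and baseline hazard after fitting.

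Under Model Tuning it states that "we considered a small learning rate (step size) of 0.01 and a large number of steps" and that "we applied 10 repeated 4-fold cross-validations to determine the hyperparameter of the boosting model". The selected number of steps is the one that "maximized the c-statistic averaged over all cross-validation iterations". No other tuning criterion is named. Then: "The final model was then fitted using all data with the optimal hyperparameter value estimated in the model-tuning exercise". For the competing cause, "separate cause-specific hazard regression models were fitted and tuned". The non-SCD death model uses 3-fold cross-validation because such deaths are few, and no different criterion is given for it.

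Under Model Performance, "both prognostic index and the 5-year cumulative proportion of SCD events were quantified for each patient". Calibration is then examined by thirds of predicted risk and by a calibration curve. Model Validation repeats the calibration curves in a separate cohort. None of these sections states a recalibration step or a shrinkage correction, or names a calibration slope.

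Protocol section 1.3 gives the objective: "To develop and validate a SCD risk calculator that is age-appropriate for children with HCM". Section 6 expects the model to bear on how closely patients are followed and on primary-prevention ICD decisions.

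**The concern.** With the step size fixed, the number of steps decides how far the coefficients are shrunk. Too few steps pull every risk towards the mean; too many make the risks too extreme. A criterion built on ranks cannot tell a well-scaled linear predictor from the same predictor multiplied by a positive constant. Where the cross-validated c-statistic is nearly flat over a range of step counts, noise chooses among models whose absolute risks differ.

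What is at stake is the spread of predicted risk, measured by the calibration slope, and so mainly the figures for children at the upper and lower ends. The c-statistic would give no warning.

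**Working it through.** **1. The protocol's event count.** Protocol section 5 gives 3,000 screened, 70-80% eligible, a 6% event rate and 100-150 events. 3,000 × 0.70 × 0.06 = 126 and 3,000 × 0.80 × 0.06 = 144, so the stated range reproduces. The period for the 6% is not stated; 5 years is assumed below.

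**2. Blindness to scale.** Risk = 1 − exp(−H × exp(k × LP)). The linear predictor LP is assumed normal with SD 1, and H is re-solved for each k so that mean 5-year risk stays at 6%. Any k > 0 leaves the ranking, and so the c-statistic, unchanged. The calibration slope implied by k is 1/k.

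| k | Slope 1/k | Mean risk by third | 95th percentile |
|---|---|---|---|
| 1 | 1.00 | 1.5 / 4.0 / 12.5% | 18.5% |
| 0.75 | 1.33 | 2.2 / 4.7 / 11.0% | 15.1% |
| 0.5 | 2.00 | 3.2 / 5.4 / 9.4% | 11.8% |
| 0.25 | 4.00 | 4.5 / 5.8 / 7.6% | 8.7% |

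This is pure rescaling. Real boosting steps also change which predictors enter and their relative weights, so the c-statistic does vary along the path. Simulation is needed to see what happens in practice.

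**3. Main simulation.** Component-wise Cox boosting with 2,100 patients and 6% events (126 expected), 10 normal predictors with linear terms, 5 repeats of 4-fold cross-validation and 40 runs per scenario. The slope was measured in 40,000 new patients. Steps are expressed as equivalents at step size 0.01.

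| Scenario | Tuned on | Slope p10 / median / p90 | Outside 0.8-1.25 | Mean c |
|---|---|---|---|---|
| One strong, rest weak or null | c-statistic | 0.97 / 1.22 / 9.36 | 45% | 0.714 |
| | partial likelihood | 0.97 / 1.06 / 1.24 | 7% | 0.715 |
| Five moderate, five null | c-statistic | 0.87 / 1.06 / 1.31 | 17% | 0.702 |
| | partial likelihood | 0.91 / 1.07 / 1.30 | 17% | 0.703 |

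In the first scenario the chosen steps ran from 200 to 12,900 (p10-p90) under the c-statistic and from 4,000 to 12,620 under likelihood. A slope of 9.36 means the log-hazard spread is about 1/9.36 = 0.11 of what it should be, which is very early stopping. In the second scenario the p90 of c-tuned steps was at the simulated limit of 40,000. A third scenario, ten equal predictors, reached that limit under both criteria and is uninformative.

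**4. Further simulations.**
- One dominant predictor, about 121 events, 40 runs: slope outside 0.8-1.25 in 68% against 10%, mean c 0.732 under both. Two moderate or graded scenarios in the same set showed little difference and were limited by the step cap.
- 2,250 patients, about 111 events, 10 repeats of 4-fold, linear terms, 120 runs per scenario. Graded effects with one stronger predictor: 35 against 18 runs outside (29% against 15%). Seven moderate predictors: 5 against 6 runs, slope SD 0.112 against 0.110, with c-tuned steps often near the simulated limit.
- 2,250 patients, about 102 events, 10 factors with splines, 62 runs: 6 against 3 runs outside (9.7% against 4.8%; unpaired Fisher p = 0.49), mean c 0.751 against 0.752. This difference is within noise.

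**The case against.** The strongest reply is that calibration is not neglected. The SAP examines it in the development data and again in an independent cohort, where risks that are too narrow or too extreme could be seen. A reader might infer from the tuning rule that calibration is ignored; the Model Performance and Model Validation sections show otherwise. What remains is that these are assessments. No section says what follows from a poor curve. Protocol section 5 allows a revised calculator, but by adding variables, which is not recalibration.

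Second, the baseline hazard is obtained after fitting, so average risk should stay about right. This stands, and it confines the point to the slope.

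Third, the benefit may be nil. It vanished with several moderate predictors, and the documents give neither the candidate list nor effect sizes. The adult model described in Protocol section 1.2 uses seven factors, so a single dominant predictor cannot be presumed. This also stands.

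Fourth, Protocol section 1.1 states the goal as discriminating risk, so the c-statistic does serve part of the purpose. That is true, but likelihood tuning gave practically the same c-statistic in every scenario reported above.

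**Conclusion.** The point holds as a weakness in the tuning criterion. Followed as written, the plan can produce 5-year risks with the wrong spread, and nothing in it would correct them. The simulated effect ran from nil with several moderate predictors to large with one dominant predictor (45% against 7%, and 68% against 10%, of runs outside 0.8-1.25).

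A reader might go further and conclude that the calculator's risks for high-risk children are wrong. The documents do not support that. They do not let anyone determine the direction or size of miscalibration, and in the spline simulation about 90% of c-tuned runs kept a slope within 0.8-1.25.

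The figures rest on an assumed predictor structure, a 6% risk read as 5-year, and complete data without competing deaths in the main simulation. The large contrasts in the main simulation come from linear terms, whereas the SAP uses splines for continuous factors. The effect of the criterion on the non-SCD death model is untested. This is a cheap improvement, not a fatal flaw.

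**What to change.** In Model Tuning, choose the number of steps for both cause-specific models by the cross-validated cause-specific partial log-likelihood, or by the integrated Brier score to 5 years. Keep the stated schemes: 10 repeats of 4-fold for SCD events and 3-fold for non-SCD death. Report the c-statistic at the chosen step count as a performance measure only. In Model Validation, add the calibration slope in the external cohort.

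The SAP is written in the past tense. If fitting is complete, rerun the tuning under the new criterion and report whether the predicted 5-year risks change.

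The cost is a short change to the SAP text, plus retuning and refitting with imputation inside each cross-validation iteration. The reported cross-validated c-statistic may be marginally lower.

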### Model Performance

On model fitting, both prognostic index and the 5-year cumulative proportion of SCD events were quantified for each patient. The discriminatory power of the final model was quantified using the c-

statistic for competing risk models. Model calibration was assessed by stratifying patients into 3 risk groups based on tertiles of the predicted 5-year probability of a SCD event and by creating a calibration curve to show the relationship between the observed and predicted 5-year probability of events.

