5. STATISTICAL ANALYSIS

5-year SCD risk score will be calculated, and discrimination and accuracy assessments will be performed. Three risk groups (low, medium, high) will be constructed using the calculated risk score. Kaplan-Meier methods with log-rank tests will be used to compare freedom from SCD; competing risk models will be applied to analyze aborted SCD events. C-statistic will be used to quantify the discriminatory ability of the risk scoring, the discrepancy between predicted and observed risk will be also assessed. A revised calculator will be generated from the test cohort using additional variables if needed. This calculator will then be tested in a validation cohort to determine its ability to predict SCD events. We anticipate screening 3,000 HCM patients across all sites of which 70-80% are anticipated to be eligible for inclusion in this analysis. We anticipate that this number will provide enough power based on anticipated SCD event rate of 6% (n=100-150) to develop a new calculator.

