6. CLINICAL RELEVANCE

Children with HCM remain at high risk for SCD. Current clinical risk factors are largely extrapolated from the adult population where a model has been developed to predict those who are at risk of SCD at 5 years^{16,17}. The ability to predict those at risk for SCD in the pediatric population using a prediction model may guide frequency of patient surveillance in those who are at higher risk and may inform indications for ICD insertion for primary prevention. Ultimately this may improve long term outcomes in this population.

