## Model Validation

The final model was externally validated using an independent replication cohort. The Harrell c-statistic was calculated, and calibration curves were constructed using quantiles of predicted risk as described above.

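### Tertiles are the only calibration grouping specified, the replication check appears to be three points, and no slope, observed/expected ratio or upper-range check is planned.

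*SAP*

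**What the plan says.** SAP, Model Performance, names two calibration elements for the final model. One is "stratifying patients into 3 risk groups based on tertiles of the predicted 5-year probability of a SCD event". The other, joined to it in the same sentence, is "by creating a calibration curve to show the relationship between the observed and predicted 5-year probability of events". It does not say whether that curve is smoothed or drawn through group means.

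SAP, Model Validation, gives one calibration statement for the independent replication cohort: "calibration curves were constructed using quantiles of predicted risk as described above". The only quantiles described earlier in the SAP are the tertiles.

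Protocol section 5 is more general. It says that "Three risk groups (low, medium, high) will be constructed using the calculated risk score" and that "the discrepancy between predicted and observed risk will be also assessed", with no cut-points and no method. Protocol section 6 gives the intended use: prediction may guide how often higher-risk children are followed, and it "may inform indications for ICD insertion for primary prevention". No risk threshold is stated.

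Neither document mentions a calibration slope or intercept, an O/E ratio, a confidence band, or a check confined to the upper range of predicted risk.

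**The concern.** For a rare outcome, predicted risks are skewed. The lower two tertiles cover a narrow span, while the top tertile takes in everything from just above average risk to the highest predictions. One observed-versus-predicted pair for that group is an average dominated by patients near its lower edge. Error confined to the highest predictions is diluted in that average, yet those predictions bear most on the stated ICD and surveillance use.

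Replication matters most here. The SAP (Model Tuning) chooses the number of boosting steps only by the c-statistic, which measures ranking and not calibration, and then fits the final model to all data. Model Performance does not say that calibration uses held-out predictions. The replication cohort is therefore the only calibration check stated to be out of sample, and it appears to rest on the coarsest grouping.

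**Working it through.** **Inputs from the documents (Protocol section 5).** 3,000 screened, 70-80% eligible, SCD event rate 6%, 100-150 events anticipated.

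**The plan's own figure.** Eligible: 3,000 × 0.70 = 2,100 to 3,000 × 0.80 = 2,400. Events: 2,100 × 0.06 = 126 to 2,400 × 0.06 = 144. Both lie inside the stated 100-150. A tertile is 700 to 800 patients; I use 750 (2,250/3). The documents give no figure for calibration itself.

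**Assumptions, because the documents give neither the risk distribution nor c.** 5-year risk follows logit(p) = a + 0.8·Z with Z standard normal and a = −3.02, which makes the mean risk 6%. For 5-year event status this gives c of about 0.71.

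**Top tertile if the model is right.** Lower cut 6.4%, 99th percentile 24%, mean 11.1%. Share of events: 11.1 / (3 × 6.0) = 62%.

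**Error put in.** Multiply predictions by 1.5 in the top 5% of patients, whose mean true risk under this model is 20.6%. Their O/E is 1/1.5 = 0.67.

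- They form 0.05/0.333 = 15% of the top tertile, so its mean prediction rises by 0.15 × 0.5 × 20.6 = 1.5 points.
- Top tertile: 12.7% predicted against 11.1% observed, O/E 0.88 (unrounded values).
- Sampling half-width: 1.96 × √(0.111 × 0.889 / 750) = 2.3 points. This is binomial; censoring before 5 years would widen it.

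**The same error in the top decile.** The affected patients are half of it. Observed 17.0%; predicted 17.0 + 0.5 × 0.5 × 20.6 = 22.2%; O/E 0.77. With 225 patients the half-width is 1.96 × √(0.170 × 0.830 / 225) = 4.9 points, so the 5.2-point gap falls just outside it.

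**Sensitivity to c, same 1.5-fold error, mean risk 6%, 750 per tertile.**

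| c | Events in top tertile | Predicted vs observed, top tertile | O/E (unrounded) | Half-width |
|---|---|---|---|---|
| 0.64 | 51% | 10.3% vs 9.2% | 0.90 | 2.1 |
| 0.71 | 62% | 12.7% vs 11.1% | 0.88 | 2.3 |
| 0.79 | 74% | 15.6% vs 13.3% | 0.85 | 2.4 |

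At c 0.60 the top tertile holds 46% of events, so it holds most of them only from c of about 0.65, or slightly below.

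**Other shapes of error, at c 0.70.** With a global calibration slope of 0.7, the top tertile shows 12.7% predicted against 10.9% true, while the top 5% shows 27.4% against 19.6%. If instead the true slope inside the top tertile is half the predicted one, with the tertile mean held correct, the tertile shows 10.9% against 10.9% while the top 5% is predicted 19.6% against 14.8% observed. Only an error that cancels within the tertile, as in this last case, disappears entirely.

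**Replication.** Its size is not given. With an assumed 200 patients per tertile the half-width is 1.96 × √(0.111 × 0.889 / 200) = 4.4 points. Even a two-fold error in the top 5% (11.1 + 0.15 × 20.6 = 14.2% predicted against 11.1%, a gap of 3.1) would lie within it, whereas with 750 per tertile it would not.

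**The case against.** The strongest reply is that the SAP does not rely on tertiles alone. It names a calibration curve as a separate element, and if that curve is smooth, much of the concern is met in development. This stands: a reader might infer that development calibration is judged only in tertiles, and the documents do not support that. They leave the curve's construction open. The validation wording, which builds curves from quantile groups, suggests the same method but does not prove it, and it does not repeat the word tertiles.

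Other stronger readings also go beyond the text:

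- That tertile cuts are recomputed in the replication cohort. The SAP does not say whether they are recomputed or carried over.
- That the error sits at an ICD decision point. No threshold is given; only the intended use can be cited.
- That a miscalibrated model would pass. The SAP has no pass/fail rule. A top-tertile O/E of 0.88 is a visible departure to an attentive reader, and under a global slope of 0.7 the lower tertiles err in the opposite direction (1.4% predicted vs 2.3% true, 3.9% vs 4.8%), which is a recognisable pattern.
- That the top tertile reaches above 30%. This needs c of about 0.75 or more; at c about 0.71 the 99th percentile is near 24%.

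It is also fair that the protocol foresees three risk groups, so a three-group display follows from it. That justifies the display. It does not make three groups an adequate calibration assessment.

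**Conclusion.** The point holds as a limitation of the stated method. Tertiles are the only grouping specified, the replication curve is most naturally three points, and nothing planned addresses slope, overall O/E or the upper range. In the illustration, an O/E of 0.67 in the top 5% shrinks to 0.88 in the top tertile (0.85-0.90 for c from 0.64 to 0.79), within sampling error for 750 patients. A smaller replication cohort would mute it further.

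The figures rest on an assumed logit-normal risk distribution, an assumed c, a mean risk of 6% and an error placed by construction in the top 5%. They show how much tertiles can dilute an error of this kind. They are no evidence that the calculator is miscalibrated. This should be changed because it is cheap and bears on the stated use; it does not invalidate the plan.

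**What to change.** State how each calibration curve is built. Then, in development (on cross-validated predictions) and in the replication cohort:

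- Assess calibration with a smooth curve for the 5-year cumulative incidence of SCD events that accounts for censoring and for non-SCD death as the competing risk, for example on pseudo-observations.
- Report the calibration slope and the overall O/E ratio with 95% CIs.
- Add O/E in the top decile, or in fixed risk bands set in development and carried unchanged into replication.
- Keep tertiles as a display only.

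The development data can support this. At 6% risk, c 0.65-0.75 and 2,100-2,400 patients, the top tenth would hold about 27-48 events. The lowest tenths would hold only about 2-5 each, which is why a smooth curve is preferable to deciles throughout.

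The cost is SAP wording and a little more analysis, with no new data. The downside is wide intervals in the upper range, especially if the replication cohort is small, and possibly a less favourable calibration picture.
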